#### 6.4 STUDY INTERVENTION COMPLIANCE

In order to complete the study intervention, the participant must have worn the PICO NPWT dressing for a minimum of 5 days after surgery. On the fifth postoperative day, the participant may remove the dressing at home. A phone call to each participant randomized to the PICO NPWT dressing will be made on the 5th or 6th postoperative day (after discharge to the hospital) to verify compliance with the use of the device. No documents are mandatory for the participants to complete and adherence to the protocol will be verified by patient report only.

#### 6.5 CONCOMITANT THERAPY

Not applicable.

##### 6.5.1 RESCUE MEDICINE

Not applicable.

### 7 STUDY INTERVENTION DISCONTINUATION AND PARTICIPANT DISCONTINUATION/WITHDRAWAL

#### 7.1 DISCONTINUATION OF STUDY INTERVENTION

Discontinuation from PICO dressing compliance before a minimum of 5 days does not mean discontinuation from the study, and remaining study procedures should be completed as indicated by the study protocol. If a clinically significant finding is identified (including, but not limited to changes from baseline) after enrollment, the investigator or qualified designee will determine if any change in participant management is needed. Any new clinically relevant finding will be reported as an adverse event (AE).

The data to be collected at the time of study intervention discontinuation will include the following:

- Reason the PICO dressing was discontinued:
  - Patient discomfort,
  - Misunderstanding of use,

- Loss of supplies,
- etc.
- Incision assessment
- SSI or SSO

## 7.2 PARTICIPANT DISCONTINUATION/WITHDRAWAL FROM THE STUDY

Participants are free to withdraw from participation in the study at any time upon request.

An investigator may discontinue or withdraw a participant from the study for the following reasons:

- Significant study intervention non-compliance
- If any clinical adverse event (AE), or other medical condition or situation occurs such that continued participation in the study would not be in the best interest of the participant
- Disease progression which requires discontinuation of the study intervention
- If the participant meets an exclusion criterion (either newly developed or not previously recognized) that precludes further study participation
- The PICO device is not compatible with MRI and cannot be taken in to an MRI suite. If the patient requires MRI, the PICO dressing will need to be discontinued

The reason for participant discontinuation or withdrawal from the study will be recorded. Subjects who sign the informed consent form and are randomized but do not receive the study intervention may be replaced. Subjects who sign the informed consent form, and are randomized and receive the study intervention, and subsequently withdraw, or are withdrawn or discontinued from the study, will be replaced.

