### 6.3 MEASURES TO MINIMIZE BIAS: RANDOMIZATION AND BLINDING

This trial tests a clinical intervention that is not amenable to protection against performance bias through the blinding of participants, clinical staff or data collectors. There will be no blinding in the study. Neither the participants nor the physicians will be blinded to the study treatment they are randomized to.

The Biostatistics Unit at the Feinstein Institute for Medical Research [BU-FIMR] will develop a randomization plan for the study using the Biostatistics Randomization Management System [BRMS]. BRMS is a secure, HIPAA-compliant, web-based application that allows investigators to randomize subjects into randomized clinical trials (RCTs) using a personal computer with internet access. The BRMS allows for multi-center, stratified, and single/double blinded RCTs. Randomization notifications are automatically sent to the PI and other authorized personnel. BRMS maintains compliance in RCTs.

A randomization schema will be generated by the BU-FIMR using the method of permuted blocks. Subjects will be randomly assigned in a 1:1 ratio to either 'PICO' or 'STANDARD DRESSING'. Details of the randomization procedure, including required record keeping will be further developed upon approval of the protocol.

The RA will randomize participants in the operating room at the start of their cesarean procedure and advise the operating obstetrician and nursing staff of the allocated treatment as close to the end of the procedure as possible in order to minimize performance bias.

To minimize the potential for outcome detection bias, an expert statistician, blinded to group allocation, will assess the data to determine the primary outcome.

Subjective outcomes (SSI/SSOs) are reported by patients or observed by study personnel, who cannot be blinded because they need to check the dressings.

Outcome assessors will be masked to allocation.

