#### 9.2 SAMPLE SIZE DETERMINATION

- Outcome measure used for calculations (almost always the primary variable): incidence of surgical site occurrences.
- Type I error rate (alpha): 0.05 (5%)
- Power level: 80%

Based on results from several clinical studies and the American Congress of OBGYN Practice Bulletin on Obesity in Pregnancy, we estimate the proportion of subjects with surgical site occurrences among obese women who undergo elective cesarean surgery to be about 18%. We accept that an absolute difference between study groups of 10%, will be a clinically meaningful difference. Therefore, a chi-square test will yield 80% power to detect a clinically important difference of 10% between study groups (SOC proportion of 18% vs. PICO NPWT proportion of 8%, an odds ratio of 0.396) when the sample size

in each group is 180 *evaluable* subjects. Assuming an attrition rate of about 10%, we would need to recruit about 200 subjects per group (180/0.90=200 subjects).

Note: A study participant is considered 'evaluable' if she has completed all phases of the study including the last visit of the last scheduled procedure in the schedule of activities, i.e. the final study visit 4—day 42±10 days post-op.

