### 9.3 POPULATIONS FOR ANALYSES

The primary statistical analysis will be based on a modified intention-to-treat (participants who underwent surgery and received the intervention). All subjects will be analyzed according to the intention-to-treat [ITT] principle. A patient will be considered evaluable and will be included in the intention-to-treat analysis if the patient has completed all phases of the study including the last visit of the last scheduled procedure in the schedule of activities, i.e. the final study visit 4—day 42±10 days post-op. Analyses that take into account the actual treatment received (e.g. use of PICO NPWT dressing for a minimum 5 days) will be carried out as a secondary analysis (per protocol [PP] analysis).

This was chosen to avoid various misleading artifacts that can arise in intervention research such as non-random attrition of participants from the study or crossover. Subjects strayed from the protocol (for instance, by not adhering to the prescribed timing of intervention, or by withdrawing from the study) will still be analyzed in the group to which they were assigned. We want to estimate the effects of using a PICO dressing at all in practice, not the effects in the subgroup of the participants who adhere to it. If patients receive a different type of dressing (intervention) accidentally from the one they were assigned, they will be excluded from the study in order to remove any bias that could arise from reasons why a provider chose to use that specific dressing instead of the assigned dressing.

In addition, a per-protocol analysis dataset will be analyzed (entire control group and PICO group who used the PICO NPWT dressing for a minimum of 5 days).

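### Section 7.2 allows withdrawal for undefined non-compliance and replaces treated women who leave; with the completers-only rule in 9.3, this can cause arm-dependent loss of primary outcomes and leaves the number randomised undefined

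*Protocol*

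**What the plan says.** Protocol section 7.2 lists reasons for which an investigator may take a woman out of the study. The first is "Significant study intervention non-compliance"; the degree that counts as significant is not defined. Others are an adverse event or other situation that makes continuing against her interest, an exclusion criterion that precludes further participation, and a need for MRI while wearing PICO. Women who were "randomized but do not receive the study intervention may be replaced", which is optional. For women who did receive the intervention the rule is mandatory: those who leave, "and subsequently withdraw, or are withdrawn or discontinued from the study, will be replaced".

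Section 7.1 takes a different line on early removal: "Discontinuation from PICO dressing compliance before a minimum of 5 days does not mean discontinuation from the study", and the remaining procedures should be completed. Section 7.3 classes women who cannot be reached as withdrawn.

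Section 9.2 provides for attrition in the sample size: "Assuming an attrition rate of about 10%, we would need to recruit about 200 subjects per group", from 180/0.90. Section 9.3 says that women who stray from the protocol, including by withdrawing, "will still be analyzed in the group to which they were assigned". The same section says a woman is evaluable and "included in the intention-to-treat analysis if the patient has completed all phases of the study", up to visit 4 at day 42 ± 10.

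On blinding, section 6.3 states: "Neither the participants nor the physicians will be blinded to the study treatment they are randomized to".

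**The concern.** The people who judge whether non-compliance is significant know which dressing the woman has. In practice that ground reaches one arm only. Section 6.4 asks for at least 5 days of PICO wear, ending at home, and checks it by a telephone call to PICO women alone. Sections 4.2 and 8.1 have the control dressing removed on postoperative day 1. The MRI item is also specific to PICO.

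If a woman who took PICO off early is withdrawn, she does not complete visit 4 and so is not evaluable under section 9.3. Should early removal be related to the state of the wound, the PICO arm would lose women at higher risk of the primary endpoint, and the comparison would favour PICO with no true effect. Enrolling another woman restores the head count but not the lost outcome.

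Separately, replacing losses that the sample size already allows for leaves it unclear how many women are to be randomised.

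**Working it through.** **1. The plan's own sample size.** Inputs from section 9.2: 18% v 8%, alpha 0.05 (taken as two-sided for a chi-square test), power 80%. With pooled variance under the null:

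n = [1.96 × √(2 × 0.13 × 0.87) + 0.842 × √(0.18 × 0.82 + 0.08 × 0.92)]² / 0.10² = (0.932 + 0.396)² / 0.01 ≈ 176.4, so 177 per arm.

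The stated 180 is within 3 of this and gives 80.8% power. 180/0.90 = 200 is the correct inflation. The arithmetic in section 9.2 is sound.

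**2. Two provisions for the same loss.** Section 7.3 counts loss to follow-up as withdrawal, so section 7.2 replaces the very women that the 10% allowance covers. Two readings are possible:

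- If 200 is the number randomised, 10% loss leaves 180 evaluable and no replacement is needed.
- If treated women who leave are replaced until 200 complete, the number randomised is 200/(1 − d) per arm: 211 at d = 5%, 222 at 10% (about 444 in total), 235 at 15%.

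The protocol does not choose. The synopsis adds to the uncertainty by giving 396 in one place and 200 + 200 in another.

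**3. How a woman leaves the primary analysis.** Early PICO removal leads to full follow-up under 7.1. Under 7.2 it can lead to withdrawal if judged significant. Under 9.3 a withdrawn woman is to be analysed as assigned, yet is not evaluable because she did not complete visit 4. The two statements in 9.3 cannot both be applied to her. Under the evaluable rule her outcome is dropped.

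**4. Possible size.** The following are assumptions, not protocol figures: no true effect; SSO risk 18% in both arms; a fraction w of PICO women withdrawn and dropped, with SSO risk r; any loss in the control arm unrelated to outcome; 180 analysed per arm. The rate among retained PICO women is

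p = (0.18 − w × r) / (1 − w).

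The chance of a significant two-sided result is then computed for p v 18% with the same normal approximation. For w = 10%:

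| r | Observed PICO rate | False-positive rate |
|---|---|---|
| 18% | (0.18 − 0.018)/0.90 = 18.0% | 5.0% |
| 30% | (0.18 − 0.030)/0.90 = 16.7% | 6.3% |
| 40% | (0.18 − 0.040)/0.90 = 15.6% | 9.5% |
| 50% | (0.18 − 0.050)/0.90 = 14.4% | 15.0% |

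Over r from 30% to 50%, the false-positive rate is 5.3% to 7.1% at w = 5% and 8.3% to 32.0% at w = 15%.

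**5. What replacement contributes.** The formula for p contains no replacement term. If the replacements are subject to the same withdrawals, the rate among completers does not change. If all of them were followed at 18% risk, the middle case would become 0.9 × 15.6% + 0.1 × 18% = 15.8%. The bias comes from losing outcomes, not from enrolling more women.

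**The case against.** Much can be said for the plan. Sections 7.1 and 7.2 are not strict opposites: one says early removal does not amount to leaving the study, the other says an investigator may withdraw a woman if non-compliance is significant. Both can stand if significant is given a meaning. That is accepted; the conflict is a practical one, because no rule separates the two outcomes.

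A reader might infer that attrition will differ by arm. The documents do not support that. Withdrawal of consent, adverse events, exclusion criteria and loss to follow-up apply to both arms; only non-compliance and MRI fall in effect on PICO. Nor does the protocol say that early removal usually follows a wound problem. The reasons that 7.1 names are discomfort, misunderstanding and loss of supplies. If those dominate, withdrawn women may have ordinary risk and the bias is nil.

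A reader might also infer that replacement conceals the loss. It does not: 7.2 requires the reason for withdrawal to be recorded, 7.1 requires an incision assessment and SSI/SSO status when PICO is stopped, and 9.4.2 reports missing data with reasons and includes all available data. But status on the day the dressing comes off is not status at day 42, and the commitment in 9.4.2 does not sit with the evaluable rule in 9.3.

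Finally, counting attrition twice costs no power. That is right; the fault there is an undefined total.

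**Conclusion.** The point holds in this form: section 7.2, applied together with the evaluable rule in 9.3, can produce arm-dependent loss of primary outcomes in an open-label trial, and it defeats the statement in 9.3 that women who withdraw are analysed as assigned. The size is unknown. With 10% of PICO women dropped, it runs from no bias to a false-positive rate of about 15%, depending on an assumed SSO risk of 18% to 50% among them. The direction favours PICO only if early removers have more wound problems than other women.

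It would go too far to conclude that replacement itself breaks intention-to-treat. It would not do so if withdrawn women stayed in the analysis. It would also be wrong to conclude that the sample size is miscalculated or the trial underpowered. Replacement merely duplicates the allowance in 9.2 and leaves the number randomised open, at about 222 per arm if 200 completers are sought at 10% attrition.

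This cannot be left to a statistical analysis plan. The withdrawal and replacement rules are explicit in the protocol, and day-42 outcomes not collected cannot be supplied by analysis.

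**What to change.** - **Section 7.2:** delete non-compliance as a ground for withdrawal from the study. Record it as discontinuation of the dressing, with follow-up to day 42 as 7.1 says. Keep women found ineligible after randomisation in outcome follow-up where they consent.
- **Section 7.2:** delete the sentence requiring replacement of treated women, and rely on the 200 randomised per group that 9.2 already provides. Reconcile the 396 and the 200 + 200 in the synopsis with that figure.
- **Section 9.3:** state that withdrawn and non-adherent women are analysed as assigned with all available outcome data, and remove completion of visit 4 as a condition for entering the analysis.
- **Clinical grounds:** the adverse-event and other clinical reasons for stopping the device or participation, including the MRI item, are for the sponsor to reconcile between 7.1 and 7.2. No change to them is proposed here.

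The cost is protocol wording. Section 8.1 describes both later visits as standard care, so following these women adds little work. With 10% loss, 180 per arm remain and power is 80.8%; if all 200 per arm are followed, it is 84.7%. The downside is slightly fewer completers if attrition exceeds 10%.

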## 7.3 LOST TO FOLLOW-UP

A participant will be considered lost to follow-up if he or she fails to return for 2 scheduled visits and is unable to be contacted by the study site staff.

The following actions must be taken if a participant fails to return to the clinic for a required study visit:

- The site will attempt to contact the participant and reschedule the missed visit within 10 days and counsel the participant on the importance of maintaining the assigned visit schedule and ascertain if the participant wishes to and/or should continue in the study.
- Before a participant is deemed lost to follow-up, the investigator or designee will make every effort to regain contact with the participant (where possible, 3 telephone calls and, if necessary, a certified letter to the participant's last known mailing address or local equivalent methods). These contact attempts should be documented in the participant's medical record or study file.
- Should the participant continue to be unreachable, he or she will be considered to have withdrawn from the study with a primary reason of lost to follow-up.

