## 8 STUDY ASSESSMENTS AND PROCEDURES

## 8.1 EFFICACY ASSESSMENTS

Screening procedures and evaluations may be performed on the day of enrollment but no more than 10 days prior to the day of enrollment. The screening process will be a discussion with the patient and review of medical history and height and weight to determine eligibility, and explanation of the study rational and study protocol, and demonstration of the two dressing options. Informed consent will then be obtained and patients will have the opportunity to ask questions.

The study intervention will be administered at the end of the scheduled cesarean delivery procedure. Standard dressings will be removed on postoperative day 1 as per current protocol and PICO NPWT dressings will be changed if necessary in the hospital and removed on postoperative day 5 by the patient at home.

**Procedures that will be completed during the study as part of regular standard of clinical care:** the post-operative visits on day 7 – 14 and 42 +/- 10 days are part of regular standard of clinical care and the outcomes and incision assessments after the participating patients leave the hospital will be performed by skilled residents and attending physicians at these visits. Charts will be reviewed to ascertain if SSO/SSIs were diagnosed or SII were necessary.

During these regularly scheduled visits, a **physical examination and incision assessment** will be performed including weight, abdominal exam, incision exam, and all regular postoperative visit exams including breast and pelvic (at the 42 +/- 10 day visit only) as part of the routine standard of care.

If follow-up visits or unscheduled visits are required for treatment of SSO/SSIs or SII, information regarding the type of SSO or SII required will be obtained from review of the medical chart.

**Surgical Site Occurrences include:** unanticipated local inflammatory response, prolonged drainage, fluid collection, dehiscence, surgical site infection (SSI). SSI is diagnosed using the following criteria: warmth to touch, pain with palpation, skin redness, irritation, or induration, large amount of drainage or purulent drainage, fluctuance suspicious for wound abscess, fever, and/or wound odor.

**Surgical Site Interventions include:** Antimicrobials for surgical site infection, surgical drainage of the incision, surgical incision packing, adjunctive negative pressure therapy, debridement, or re-operation.

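### An unreachable woman is classed as withdrawn, replaced and left out as a non-completer even if her chart already shows an SSO, while other sentences of the protocol say she is analysed

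*Protocol*

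**What the plan says.** Protocol 7.3 defines a participant as lost to follow-up if she "fails to return for 2 scheduled visits and is unable to be contacted by the study site staff". Its action list starts after a missed required visit, asks for rescheduling within 10 days, then up to three calls and, if necessary, a certified letter. If she remains unreachable, "he or she will be considered to have withdrawn from the study with a primary reason of lost to follow-up".

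Protocol 7.2 covers women who were randomised and treated and who then withdraw, "or are withdrawn or discontinued from the study, will be replaced".

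Protocol 8.1 names the outcome source: "Charts will be reviewed to ascertain if SSO/SSIs were diagnosed or SII were necessary". It adds that for follow-up or unscheduled wound visits the type of SSO or SII comes from the medical chart. Post-discharge incision assessments are made by clinicians at the routine visits on days 7–14 and day 42 ± 10.

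Protocol 9.2 calls a woman evaluable only if she completed all phases including Visit 4. It sets 180 evaluable per group and then inflates: "Assuming an attrition rate of about 10" per cent, hence 200 recruited per group.

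Protocol 9.3 makes that completion the condition for entering the intention-to-treat analysis. The same section says that women who stray from the protocol, including by withdrawing, are still analysed in their assigned group. Section 9.4.2 handles loss to follow-up by reporting the data as missing, with the reason, and including all available data.

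**The concern.** The test applied in 7.3 is contact with the woman, not whether her outcome is known. The two can differ: a wound problem seen on the ward or at an unscheduled visit is already in the chart when the calls go unanswered. She has asked for nothing, yet she receives the same status as a woman who withdraws at her own request.

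Three rules then act together. The 7.3 label makes her a withdrawal, 7.2 has her replaced, and the completer condition leaves her out. Section 7.1 says that stopping the dressing early does not end study participation and that the remaining procedures continue. Neither 7.2 nor 7.3 says anything similar about a woman classed as withdrawn from the study.

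Whether a woman returns or can be reached may depend on how her wound healed and, in an open-label trial, on which dressing she had. Leaving out known outcomes on that basis, and enrolling substitutes, weakens the comparison that randomisation was meant to protect. A lesser issue is that losses reported under 7.3 could be taken as the attrition that 9.2 allows for, although they count something else.

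**Working it through.** **1. The plan's own figure.** Inputs from 9.2: 18% v 8%, alpha 0.05, and the statement that "a chi-square test will yield 80% power to detect a clinically important difference of 10% between study groups". Sidedness is not stated; two-sided fits. With mean proportion 0.13:

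n = [1.960·√(2·0.13·0.87) + 0.842·√(0.18·0.82 + 0.08·0.92)]² / 0.10² = (0.932 + 0.396)² / 0.01 ≈ 177 per group.

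The plan states 180, which gives 80.8% power, and 180/0.90 = 200. The sample size is sound on its own inputs.

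**2. One woman followed through the text.** She has an SSO charted at an unscheduled visit, misses Visits 3 and 4, and cannot be reached.

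- 8.1: her SSO is obtainable from the chart.
- 7.3: she is considered withdrawn.
- 7.2: she is replaced.
- 9.2 and the completer sentence of 9.3: not evaluable, not in the analysis.
- The adherence sentence of 9.3: analysed in her assigned group.
- 9.4.2: available data included.

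The last two lines cannot be reconciled with the fourth.

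**3. When the label falls.** Only Visits 3 and 4 appear to require a return, since the day 1 visit is on the ward. Under the first sentence of 7.3 she must miss both, so the label falls near the end of the window (42 + 10 = day 52). If the action list is read as running from a single missed visit, a woman who misses Visit 3 by day 14 and is not rescheduled within 10 days could be labelled from about day 24, which is 52 − 24 = 28 days before the window closes.

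**4. A 7.3 count against a Visit 4 count.** Under the first sentence, women lost by 7.3 are a subset of women without Visit 4. Assumed miss rates, independent between visits:

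| Miss Visit 3 | Miss Visit 4 | Miss both (ceiling for 7.3) | No Visit 4 | Miss either |
|---|---|---|---|---|
| 10% | 10% | 0.10 × 0.10 = 1% | 10% | 1 − 0.90 × 0.90 = 19% |
| 10% | 15% | 0.10 × 0.15 = 1.5% | 15% | 1 − 0.90 × 0.85 = 23.5% |

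The last column applies if completing all phases also requires Visit 3. Without independence, missing both can rise to the smaller of the two rates (10% in each row), and the requirement that she be unreachable lowers the 7.3 count again. If 15%, 20% or 25% of 200 were not evaluable, n would be 170, 160 or 150 per group and power 78.5%, 76.0% or 73.3%.

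**5. Direction of bias.** The planned rates give 36 v 16 events among 200 per group. Suppose 20 per group have no Visit 4 and the completer condition removes them together with their events. The splits are assumed; the documents give none.

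- 3.6 v 1.6 events removed: 32.4/180 = 18.0% v 14.4/180 = 8.0%, no bias.
- 8 v 1.6 removed: 28/180 = 15.6% v 8.0%, difference 7.6 points.
- 0 v 4 removed: 36/180 = 20.0% v 12/180 = 6.7%, difference 13.3 points.

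The true difference is 10 points, so the error can go either way. These figures concern all women without Visit 4, not only those labelled under 7.3.

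**6. What keeping outcomes could add.** If outcomes were known for half or all of the 20, n would be 190 or 200 and power 82.9% or 84.7%. These are ceilings, because charts will not settle every woman's outcome.

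**The case against.** The strongest reply is that 7.3 only assigns a disposition label. A reader might infer that outcome collection stops there and that recorded SSOs are lost. The text does not say so: the chart review in 8.1 carries no condition on contact, and 9.3 and 9.4.2 contain sentences that keep the woman and her data. This stands. Exclusion arises only when 7.3 acts together with 7.2 and the completer condition, and those contrary sentences make it a contradiction, not a certain loss. But 9.4.2 can use only data that were abstracted, and nothing expressly requires abstraction after the label is applied.

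Timing also limits the harm. The natural reading of 7.3 is an escalation that ends in the two-visit definition, and then little collection time remains. The single-visit reading is possible but less natural.

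Charts are not a full substitute either. Without a visit there is no incision examination, so a woman who missed both visits has only ward or unscheduled-visit entries. The protocol does not say that care elsewhere is captured.

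Finally, 9.2 defines evaluability and never equates attrition with 7.3 losses. That is correct: the two rules serve different purposes, and the sample size contains no error on this account. What remains is that a 7.3 count is the wrong one for monitoring the allowance.

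**Conclusion.** The point holds as an unresolved contradiction with a practical consequence. Read one way, the protocol withdraws, replaces and omits an unreachable woman whose SSO is already charted; read another way, it analyses her. Until this is settled, charted outcomes may be left out in a way related to outcome and arm.

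No size or direction can be given. A reader might go further and build a case in which the lost women overturn a significant result. That needs an SSO rate among lost PICO women far above the planned 8%, which nothing in the documents supports. It also needs all 20 planned losses per group to fall under 7.3, although the two-visit rule could cover as few as 1% (2 of 200) under the independence assumption above. The splits in the working show only that the direction is open.

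The sample size is not in question. The mismatch with 9.2 is a caution about which count to monitor. The change is worth making because it is cheap and uses a chart review that is already planned.

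**What to change.** - In 7.3, record an unreachable woman as lost to contact, not withdrawn. Limit withdrawal from data collection to a woman's own request.
- In 7.2, state that women lost to contact are not replaced; the 10% inflation already allows for them.
- In 8.1, state that the chart of every randomised, non-withdrawn woman is reviewed to day 52 whatever her attendance or contact status, and that any charted SSO or SII counts in her assigned group.
- In 9.3, align the completer sentence with this rule, so that it no longer conflicts with the sentence on withdrawn women or with 9.4.2.
- Report women with no charted event and no Visit 4 as missing, and vary their outcome in a sensitivity analysis. The detail can go in the SAP.
- Monitor the 10% of 9.2 on women without a primary outcome, and report women lost to contact separately.

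The cost is protocol wording plus chart abstraction that 8.1 already foresees. There is a small downside: a chart without a visit cannot prove freedom from SSO, so charts alone tend to add events only. The missing status and the sensitivity analysis are there for that reason.
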